OFFICIAL TITLE:

"Intraoperative Continuous Noninvasive Hemoglobin Monitoring in Patients Undergoing Thoracic Surgery"

NCT NUMBER: still not available

DOCUMENT DATE:

July 13, 2024

Intraoperative continuous noninvasive hemoglobin monitoring in patients undergoing thoracic surgery.

Background: hemoglobin levels similar to how a pulse oximeter provides continuous oxygen saturation. The spot check hemoglobin monitor works by the same principle as the continuous monitor but is a point-of-care device that calculates the serum hemoglobin level within 1 min of placement of the probe. The accuracy and reliability of both these monitors vary and the clinical applicability in trauma remains to be defined. Accuracy of continuous non-invasive hemoglobin monitoring.

Methods: This observational study evaluated the correlation between noninvasive hemoglobin monitoring (SpHb) and invasive hemoglobin measurements (InvHb) in guiding blood transfusions during thoracic surgery. A total of 80 patients aged 18 years or older, all scheduled for thoracic procedures between July 2024 and July 2025, were enrolled. Continuous SpHb monitoring was performed throughout the surgeries, with simultaneous InvHb samples collected to validate the readings. The primary outcome will be the degree of correlation between SpHb and InvHb values.

Introduction:

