Invasive measurement, although accurate is time-consuming, costly, painful for the patient, and may have potential risk for exposure to biohazards. It can significantly delay patient care because of the time required for the phlebotomy, transport of the sample to the laboratory, time required for analysis and validation, and the reporting of results back to physician. Hemoglobin (Hgb) measurement is one of the most frequently ordered laboratory tests in the trauma settings; it can help guide therapeutic plan of management [1]. In trauma patients, these decisions range from blood transfusions to operative intervention. There has been a significant paradigm shift towards non-operative management in trauma patients and the rate of operative intervention in blunt abdominal and pelvic trauma has significantly declined. The majority of these patients are managed non-operatively and undergo surgical intervention only for ongoing bleeding or hemodynamic instability [3,4]. This approach however requires close monitoring in the Intensive Care Unit (ICU) and repeated phlebotomy for hemoglobin measurement to assess for ongoing hemorrhage [5]. The use of continuous or spot-check non-invasive hemoglobin monitoring provides the ability to monitor these patients in real time and react to changes in hemoglobin levels. A Cochrane review from ten trials reported outcomes on 1780 patients and found that a restrictive transfusion strategy is associated with 20% lower mortality, reduced hospital and ICU length of stay [6]. On the other hand, post operative anemia is also associated with increased post operative morbidity and mortality [7]. Accurate continuous measures of hemoglobin can help avoid the extremes of over or under transfusion. This is another avenue where a quick non-invasive measurement of hemoglobin can help in the implementation of restrictive transfusion strategy.

3. Basics of function

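### Does naming only the correlation of SpHb and InvHb as the outcome leave the study unable to show that the monitor follows hemoglobin change during surgery?

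*Protocol*

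**What the plan says.** The Methods paragraph in the protocol's opening summary carries the whole design. It describes an observational comparison of noninvasive (SpHb) with invasive (InvHb) hemoglobin, in terms of their correlation, "in guiding blood transfusions during thoracic surgery". The sampling is given in one sentence: "Continuous SpHb monitoring was performed throughout the surgeries, with simultaneous InvHb samples collected to validate the readings". The size is "A total of 80 patients aged 18 years or older", without a derivation. One outcome is named: "The primary outcome will be the degree of correlation between SpHb and InvHb values".

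The protocol does not give the number of simultaneous pairs per patient. It does not say whether the coefficient is computed across all pairs, within patients or on changes.

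The Introduction says that continuous or spot-check devices give a facility that "provides the ability to monitor these patients in real time and react to changes in hemoglobin levels". The patients meant there are trauma patients managed without operation. The same section adds: "Accurate continuous measures of hemoglobin can help avoid the extremes of over or under transfusion". Both sentences are background on the technology, and neither is worded as an aim of this study.

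**The concern.** A continuous monitor is chosen over a spot check because it can show hemoglobin moving. The title stresses continuous intraoperative use and the Methods paragraph mentions transfusion guidance, so a reader may expect the result to bear on whether the monitor follows a fall or a rise during the operation.

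A single correlation over all pairs cannot establish that. If patients enter surgery with clearly different hemoglobin levels, a device that ranks them correctly earns a high coefficient even when it misses every change after the first reading. A report that cited a high pooled r as evidence of tracking would be drawing an unsupported conclusion about the use for which the device is worn.

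**Working it through.** **Inputs.** From the protocol: 80 patients, simultaneous pairs, a correlation as outcome. It gives no SDs and no number of pairs per patient. All SDs below are therefore assumptions, in g/dL. The 80 cannot be reproduced, because no power, alpha or target correlation is stated.

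**Model.** Let sb be the between-patient SD, sw the within-patient SD, n the device-noise SD, and k the fraction of within-patient change that the monitor follows (0 none, 1 all).

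- Pooled r = (sb² + k·sw²) / √[(sb² + sw²)(sb² + k²·sw² + n²)]
- Within-patient r = k·sw / √(k²·sw² + n²)

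**Step 1: is the statistical point true?** Take sb 1.5, sw 0.7, n 0.5.

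- k = 0: 2.25 / √(2.74 × 2.50) = 0.86; within-patient r = 0.
- k = 0.5: (2.25 + 0.245) / √(2.74 × 2.6225) = 0.93; within-patient r = 0.35 / √0.3725 = 0.57.
- k = 1: 2.74 / √(2.74 × 2.99) = 0.96; within-patient r = 0.7 / √0.74 = 0.81.

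So yes: 0.86 can arise with no tracking at all.

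**Step 2: how ambiguous is a pooled r?** Use the grid sb {1, 1.5, 2}, sw {0.5, 0.7, 1, 1.5}, n {0.5, 0.7, 1}, which has 36 combinations. Pooled r runs from 0.39 to 0.94 with no tracking and from 0.75 to 0.98 with full tracking. The overlap, 0.75 to 0.94, looks wide. It arises partly from comparing a non-tracking monitor in one patient population with a tracking monitor in another. At identical SDs the tracking monitor always scores higher, by 0.03 to 0.48 (median 0.14).

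Both monitors would be worn by the same patients, so sb and sw should be held fixed and only device noise varied:

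| sb / sw | No tracking | Full tracking | Overlap |
|---|---|---|---|
| 1.0 / 0.5 | 0.63–0.80 | 0.75–0.91 | yes |
| 1.0 / 0.7 | 0.58–0.73 | 0.77–0.92 | no |
| 1.0 / 1.0 | 0.50–0.63 | 0.82–0.94 | no |
| 1.0 / 1.5 | 0.39–0.50 | 0.87–0.96 | no |
| 1.5 / 0.5 | 0.79–0.90 | 0.85–0.95 | yes |
| 1.5 / 0.7 | 0.754–0.860 | 0.856–0.957 | yes, barely |
| 1.5 / 1.0 | 0.69–0.79 | 0.87–0.96 | no |
| 1.5 / 1.5 | 0.59–0.67 | 0.90–0.97 | no |
| 2.0 / 0.5 | 0.87–0.94 | 0.90–0.97 | yes |
| 2.0 / 0.7 | 0.84–0.92 | 0.90–0.97 | yes |
| 2.0 / 1.0 | 0.80–0.87 | 0.91–0.98 | no |
| 2.0 / 1.5 | 0.72–0.78 | 0.93–0.98 | no |

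Five of 12 settings overlap, all with sw of 0.7 or less. Where hemoglobin moves most, the pooled coefficient separates the two extremes.

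**Step 3: does the protocol make the error?** Set the aim beside the outcome. The aim is the correlation between the two measurements, with invasive samples drawn to validate the readings. The outcome is the degree of that correlation. They match. For a misleading result, three further things must hold:

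1. The coefficient is pooled. The protocol does not say so, and the choice between pooled, within-patient and change-based correlation is commonly left to a statistical analysis plan.
2. Each patient gives at least two pairs. This is not stated. With one pair each, there is no within-patient change in the data to be mixed in.
3. The report concludes that the monitor follows change. The protocol announces no such conclusion.

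**The case for a change.** The strongest reply is that the outcome and the paired sampling are fixed in the protocol, whatever a later plan adds. A study titled for continuous monitoring and set in the context of transfusion invites a tracking reading, and a sentence limiting conclusions to levels would cost almost nothing. If only one pair per patient is taken, tracking cannot be assessed at all, so the limit would apply then too.

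The separation in the table also depends on there being no patient-specific device offset. Adding an offset of SD 1.0 to the fully tracking monitor at 1.5/0.7/0.5 lowers its pooled r from 0.96 to 0.83. That is below the 0.86 of a non-tracking monitor without offset, so with unequal offsets the ambiguity widens again. Partial tracking lies between the two extremes and is harder still to tell apart.

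What stands: a pooled correlation does not by itself establish tracking, and trending is a reasonable question for such a device. What does not follow is a fault in the document. The non-tracking monitor is an idealised limit, one that reads differences between patients correctly and ignores every change within them. The protocol's account of the optical method, in the section on non-invasive hemoglobin monitors, gives no reason to expect that split. Asking for a trending outcome, or for a disclaimer on a claim nobody has made, is a preference about scope.

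**Conclusion.** The concern does not hold. The outcome fits the stated aim, conclusions about hemoglobin levels are unaffected by this point, and carrying out the plan as written gives no wrong result on it. The caution is valid only for a tracking claim that the protocol does not make, and only under conditions that it does not state.

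On size, a pooled r of 0.86 with no tracking is possible under assumed SDs, but nothing shows that a misleading value is likely here. The 5-of-12 overlap rests on the assumed grid, on no device offset, and on comparing the extremes of no and full tracking. The main ground is the match between aim and outcome, which needs none of these assumptions. Whether a correlation is enough to judge bias or agreement in levels is a separate question and is not settled here.
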